## **6.4. Physical Examination and Medical History**

Physical examination findings will be collected at screening, day 1 of each infusions, surgery and end of treatment. Medical and surgical history will also be collected during screening.

Physical examination and medical history data will not be analyzed and displayed in this SAP. The weight and height will be summarized in baseline characteristics table.

## **6.5. Electrocardiogram**

ECG will be obtained during screening. ECG data will not be analyzed and reported in this SAP.

## **7. GENERAL STATISTICAL CONSIDERATIONS**

This section will go into detail about the statistical approaches and methodology for this study analysis. Statistical analysis and programming of tables and listings will be conducted by QDS, using SAS® Release 9.4 (SAS Institute Inc., Cary, North Carolina, USA).

### **7.1. Study Design and Sample Size Considerations**

This is a Phase Ib study evaluating whether the addition of lirilumab to nivolumab is feasible and safe in patients with cisplatin-ineligible muscle-invasive urothelial carcinoma of the bladder in the neoadjuvant therapy setting. Eligible patients will be assigned sequentially to either nivolumab monotherapy in Cohort 1, and if there is no negative safety signal (assessed by interim safety analyses) after the first 12 patients, subsequent patients will be assigned to Cohort 2 treated with nivolumab/lirilumab.

There will be 12 patients in cohort 1 treated with nivolumab and 24 patients in cohort 2 treated with nivolumab+ lirilumab for the final analysis.

### **7.2. Methodology**

Continuous data will be summarized with the following descriptive statistics: number of observations (n), mean, standard deviation (SD), median, minimum (min), and maximum (max). Categorical data will be summarized with frequencies and percentages. Hypothesis testing for categorical data will use nonparametric methods.

In general, listings will be presented by patient. Tables will be summarized and presented by cohort in specific analysis populations.

### **7.3. Handling of Dropouts or Missing Data**

All attempts will be made to prevent any missing values. Missing or invalid data will be treated as missing, not imputed.

No data imputation will be done for safety parameters except for the adverse events (AEs) with missing starting date. If the AE onset date is unknown, then the date of first study treatment will be used for classification of AEs that were experienced following administration of study drug. If the relationship between AE and study medication (nivolumab or lirilumab) is missing, then the “related” is assigned in the AE analysis.

### **7.4. Endpoints**

#### **7.4.1. Primary Endpoint**

The primary endpoint of this study is the rate of Grade 3 or higher adverse events during neoadjuvant treatment.

Analytic Plan for Primary Objective: The rates of Grade 3 or higher treatment-related AE during neoadjuvant treatment will be reported along with 90% exact binomial confidence intervals. In Cohort 1 the maximum width of the confidence interval is 0.51 while in Cohort 2 it is 0.36.

#### **7.4.2. Secondary Endpoints**

The secondary objective endpoints for this study are listed below:

##### **7.4.2.1. The key secondary endpoint is the change in tumor-infiltrating CD8+ T-cell density from TURBT to radical cystectomy in each cohort**

Analytic Plan for This Key Secondary Objective:

In each cohort, a one-sample Wilcoxon signed-rank test will be used to test whether the mean change in TIL density differs significantly from zero. Our hypothesis is that the change in TIL density between TURBT and radical cystectomy will be approximately 3.0 CD8+ TILs per 100 tumor cells within HPF.

Additionally, the TIL density at radical cystectomy will be compared between the two cohorts using a Wilcoxon rank sum test.

**7.4.2.2. The average percentage (%) change in the CD8+ TIL density from TURBT to RC in each of the two cohorts. Each individual patient's percent change will be defined as [(Cystectomy TIL Density) – (TURBT TIL Density)] / (TURBT TIL Density).**

Analytic Plan for this secondary endpoint: The mean percent change of CD8+ TIL density from pre-treatment (TURBT) to post-treatment (Radical Cystectomy, RC) samples in all 12 patients in Cohort 1 and all 24 patients in Cohort 2 will be calculated and compared between the two cohorts using a Wilcoxon rank sum test.

**7.4.2.3. Proportion of patients in each cohort who do not get a radical cystectomy specifically and directly related to treatment related AEs within 6 weeks of the last dose of neoadjuvant treatment.**

Analytic Plan for this secondary endpoint: The proportion of patients in each treatment cohort who do not get radical cystectomy specifically and directly related to treatment related AEs within 6 weeks of the completion of neoadjuvant treatment, will be reported along with exact binomial 90% confidence intervals for each cohort and compared between the two cohorts using Fisher's exact test.

**7.4.2.4. Proportion of patients with pathologic complete (pT0N0) and partial (<pT2N0) response in the two cohorts.**

Analytic Plan for this secondary endpoint: The proportion of patients in each treatment cohort with pathologic complete response (CR) and pathologic partial response (PR) will be reported along with exact binomial 90% confidence intervals for each cohort

**7.4.2.5. Proportion of patients who are alive and free of disease in each cohort at 2 years from registration.**

Analytic Plan for this secondary endpoint: Recurrence-free survival (defined as patients who are alive and without evidence of disease recurrence) from the time of registration will be estimated using Kaplan-Meier method for each treatment cohort and compared between the two cohorts using a log-rank test. The two-year disease-free survival estimates and confidence intervals will be provided for each cohort.

**7.4.2.6. The relationship between the expression of baseline IHC markers of interest (e.g. PD-1, PD-L1, PD-L2, NKG2D, KIR2DL1/2/3), and change in expression, for pathologic partial and complete tumor response (defined by cystectomy pathologic staging <pT2N0 and pT0N0, respectively), in patients treated with nivolumab and combination of nivolumab/lirilumab. To also compare the association of study cohort and pathologic response stratified by levels of expression of these biomarkers of interest.**

Analytic Plan for this secondary endpoint: As a general strategy, IHC marker levels in responders vs. non-responders will be compared by a t-test or Wilcoxon rank sum test as appropriate. In addition to evaluating expression on a continuous scale we will explore quantile values for each marker as potential thresholds to discretize the marker levels. The two-year RFS will then be compared between marker groups with a Fisher's exact test as well as via time-to-event analyses using standard methods for survival analysis. Changes in biomarker levels will be computed and compared between groups using a Wilcoxon rank sum test.

**7.4.2.7. The relationship between peripheral blood mononuclear cell (PBMC) T-cell subset status (%CD4+ T-cells, %CD8+ T-cells, %Treg T-cells, %Myeloid Derived Suppressor Cells, %Natural Killer cells, etc.) and change in status, as assessed by flow cytometry analysis, for pathologic partial and complete tumor response (defined by cystectomy pathologic staging < pT2N0 and pT0N0, respectively), in patients treated with nivolumab and combination of nivolumab/lirilumab.**

Analytic Plan for this secondary endpoint: The PBMC T-cell subset status in responders vs. non-responders will be compared by a t-test or Wilcoxon rank sum test as appropriate.

### **7.4.3. Exploratory Objective Endpoints**

**7.4.3.1.** To compare the CD8+ TIL density at radical cystectomy between the patients treated with nivolumab and combination of nivolumab/lirilumab.

**7.4.3.2.** The prognostic and predictive relationship between pre- and post- treatment TIL and NK-cell level and activation and pathologic partial and complete response (defined by cystectomy pathologic staging <pT2N0 and pT0N0, respectively) as well as two-year RFS, in patients treated with nivolumab and combination of nivolumab/lirilumab.

**7.4.3.3.** To assess impact of prior BCG exposure on rates of pathologic partial and complete response (defined by cystectomy pathologic staging <pT2N0 and pT0N0, respectively) as well as two-year RFS, in patients treated with nivolumab and combination of nivolumab/lirilumab.

**7.4.3.4.** To assess the prognostic and predictive relationship of tumor mutational load, neo-epitope burden, intrinsic molecular subtypes (basal vs. luminal), and T-cell clonality with pathologic partial and complete response (defined by cystectomy pathologic staging <pT2N0 and pT0N0, respectively) as well as two-year RFS, in patients treated with nivolumab and combination of nivolumab/lirilumab

**7.4.3.5.** To assess the prognostic and predictive relationship of pre- and post-treatment T-cell subsets, CD4+/CD8+ and CD4+/FOXP3+ ratios and plasma cytokine multiplex panels with pathologic partial and complete response (defined by cystectomy pathologic staging <pT2N0 and pT0N0, respectively) as well as two-year RFS, in patients treated with nivolumab and combination of nivolumab/lirilumab.

**7.4.3.6.** To assess the prognostic and predictive relationship between pre- and post-neoadjuvant treatment levels in plasma cytokine biomarkers of interest (e.g. IFN- $\alpha$ , TGF- $\beta$ , IL-10, IL-4, IL-5, IL-13, IFN- $\gamma$ , etc.) and pathologic partial and complete response (defined by cystectomy pathologic staging <pT2N0 and pT0N0, respectively) as well as two-year RFS, in patients treated with nivolumab and combination of nivolumab/lirilumab.

**7.4.3.7.** To assess prognostic and predictive associations between baseline tumor and/or tumor infiltrating lymphocyte tissue and ctDNA genomic alterations, gene expression, and methylation signatures for pathologic partial and complete response (defined by cystectomy

pathologic staging <pT2N0 and pT0N0, respectively) as well as two-year RFS, in patients treated with nivolumab and combination of nivolumab/lirilumab.

**7.4.3.8.** To assess prognostic and predictive value of serum circulating antibody profiles on pathologic partial and complete response (defined by cystectomy pathologic staging <pT2N0 and pT0N0, respectively) as well as two-year RFS, in patients treated with nivolumab and combination of nivolumab/lirilumab.

**7.4.3.9.** To assess CD8+ TIL density by central pathology review using image analysis in TURBT and radical cystectomy in each arm

## **7.5. Analysis Populations**

The study will aim to screen 43 eligible patients in order to enroll 36 patients in the trial. There will be 12 patients in cohort 1 and 24 patients in cohort 2. There will be a safety population for safety analysis and an efficacy population for efficacy analysis.

### **7.5.1. Safety Population**

The safety population is defined as all patients treated with at least one dose of nivolumab and/or lirilumab. It is the same as “Evaluable for Toxicity” population that used in protocol. All safety data collected up to the end of the study (i.e., through the last follow-up evaluation) are included in the safety analysis.

### **7.5.2. Efficacy Population**

The efficacy population is defined as all patients who received at least one dose of trial therapy, undergo radical cystectomy and have at least one of the following tumor evaluations listed below. Patients who exhibited objective disease recurrence prior to the end of treatment will also be considered as part of the efficacy population.

Below is the list of tumor evaluations:

1. CD8+ T-Cell Density

2. %CD8+ Tumor-Infiltrating T-Cells
3. Pathologic Tumor Response
4. Tumor IHC Staining Intensity Definitions

## **7.6. Safety Analysis**

The safety evaluations include AEs, concomitant medication, clinical laboratory assessments, vital signs, and physical examination. Safety analysis will be assessed for the safety population.

The results of this study will be reported using summary tables, figures, and data listings. Continuous variables will be summarized using mean, SD, median, minimum, and maximum. Categorical variables will be summarized by presenting the number (frequency) and percentage in each cohort.

If any screening safety data is repeated, the measurement taken closest to dosing will be used in the analysis as pre-study baseline. If any post-dose safety data is repeated, the measurement taken first at the particular visit in question will be used in the analysis.

### **7.6.1. Disposition**

Disposition data (e.g. informed consent, treated patients, surgery, etc.) will be summaries descriptive by cohort and overall patients for the patients who enrolled into the study. Patients who signed informed consent and registered are considered as enrolled into the study.

### **7.6.2. Demographics and Baseline Characteristics**

Demographic data (e.g. age, gender, race, height, screening body weight, cancer pathology, etc.) will be summarized descriptively (number of patients (frequency), mean, SD, median, minimum, and maximum) by cohort and overall in the safety population.

### **7.6.3. Medical and surgical History**

Medical and surgical history data (e.g. surgical procedure, prior cancer therapy signs and symptoms, etc.) that collected during screening will be summaries by cohort and overall.

### **7.6.4. Concomitant Medications and Procedure**

The use of concomitant medications and procedure will be recorded on the CRFs. The concomitant medications will be coded to a World Health Organization Drug Dictionary (WHO-DD) term.

The use of concomitant medications and procedures will be summarized by cohort and overall group for the safety population. In each of these summary tables, the number and percentage of patients taking each medication will be presented by ATC Classification.

### **7.6.5. Study treatment and Surgery**

The count and percentage of Nivolumab and Lirilumab administration completion and dose delay by cohort will be displayed. The number of patients who receive radical cystectomy will be summarized as well,

### **7.6.6. Adverse Events**

#### **7.6.6.1. Primary Endpoint, Grade 3 or Higher Treatment-related AE**

The rates of Grade 3 or higher treatment-related AE during neoadjuvant treatment will be reported along with 90% exact binomial confidence intervals.

#### **7.6.6.2. Secondary Endpoint, Patient who Did not Get Radical Cystectomy Due to AE**

The proportion of patients in each treatment cohort who do not get radical cystectomy specifically and directly related to treatment related AEs within 6 weeks of the completion of neoadjuvant treatment, will be reported along with exact binomial 90% confidence intervals for each cohort and compared between the two cohorts using Fisher's exact test. This is one of secondary objective endpoints.

The Identification of the AEs that cause patients do not get radical cystectomy by selecting "Caused Study Discontinuation" in AE CRF page, and with related to Nivolumab/Lirilumab, and patients do not have radical cystectomy surgery.

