2.2 Secondary Objectives

- To assess the change in CD8+ TIL density from pre-treatment Transurethral Resection of Bladder Tumor (TURBT) to post-treatment Radical Cystectomy (RC) tissues separately in patients treated with nivolumab or combination of nivolumab/lirilumab.
- To assess percentage (%) change in CD8+ TIL density from pre-treatment TURBT to post-treatment RC tissues separately in patients treated with nivolumab and combination of nivolumab/lirilumab.
- To describe the rate of patients in each cohort who do not get RC within 6 weeks after completion of neoadjuvant treatment specifically and directly related to treatment-related adverse events (AEs).
- To assess the antitumor efficacy of nivolumab and combination of nivolumab/lirilumab as measured by pathologic complete (pT0N0) and partial (<pT2N0) response rate in the two cohorts.
- To assess the rate of recurrence-free survival (RFS) at the two-year time point from the time of registration in patients treated with nivolumab and combination of nivolumab/lirilumab.

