8.2 Duration of Follow-Up

Patients will be followed for adverse events for 100 days after their last dose of neoadjuvant treatment. Adverse events may be reviewed at the next visit \geq 100 days after last dose of neoadjuvant therapy or phone follow-up may be done to review adverse events. However, if a patient experiences an adverse event $>$ 100 days after their last dose of study medication that is felt to be, in the opinion of the investigator, possibly, probably or definitely related to study therapy, the adverse event should be reported.

Patients will be followed clinically and radiographically per standard of care (3 -6 months) at the discretion of the treating physician for at least 2 years post-cystectomy or when study-wide follow-up ends. Date of diagnosis for progression, first subsequent therapy and survival shall be reported. Phone follow-up may also be done for patients unable or unwilling to return for follow-up evaluations.

If a patient is removed from treatment for reason(s) other than progression, follow with regular tumor assessments per standard of care until progression or start of new treatment.

For patients who are registered but do not receive any protocol therapy, baseline and follow-up information per Section 11 will be collected.

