13.2.3 Additional Secondary Objectives

1. The average percentage (%) change in the CD8+ TIL density from TURBT to RC in each of the two cohorts. Each individual patient's percent change will be defined as $[(\text{Cystectomy TIL Density}) - (\text{TURBT TIL Density})] / (\text{TURBT TIL Density})$.
2. Proportion of patients in each cohort who do not get a radical cystectomy specifically and directly related to treatment related AEs within 6 weeks of the last dose of neoadjuvant treatment.
3. Proportion of patients with pathologic complete (pT0N0) and partial (<pT2N0) response in the two cohorts.
4. Proportion of patients who are alive and free of disease in each cohort at 2 years from registration.

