#### **7.6.6.3. AE Summary Analysis by System Organ Class and Preferred Term**

Treatment-emergent AEs (TEAEs) are those that occur after administration of the first study dose until 100 days after last dose of study medication. In the case where the start date of the AE is unknown, it will be assumed to be treatment-emergent. TEAEs will be summarized by System Organ Class (SOC) and preferred term (PT) using the Medical Dictionary for Regulatory Activities (MedDRA®). The latest version of MedDRA (V 20.0) will be used. The frequency of patients who experience TEAEs will be summarized by cohort and overall. Patients, having the same AE more than once per group, will be counted once for each PT and once within each SOC.

All AEs, TEAEs, treatment-related AEs, Grade 3 or higher treatment-related AEs, SAEs, TEAEs caused stopping study medications, TEAEs leading to early termination, fatal TEAEs will be summarized by cohort and overall group. Also, above AE categories will be summarized by SOC and PT as well.

Common Terminology Criteria for Adverse Events version 5.0 (CTCAE v5.0) will be used to manifest AE grade.

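### The SAP rule for counting cystectomies missed because of drug toxicity has no 6-week test and depends on a study-discontinuation flag, so it does not measure the defined endpoint

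*SAP*

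**What the plan says.** Protocol 2.2 states the objective as describing the rate of patients "who do not get RC within 6 weeks after completion of neoadjuvant treatment specifically and directly related to treatment-related adverse events (AEs". SAP 3.2 repeats it. Protocol 13.2.3 carries the same window and counts it from the last dose: patients "who do not get a radical cystectomy specifically and directly related to treatment related AEs within 6 weeks of the last dose of neoadjuvant treatment". Protocol 13.2.3.1, SAP 7.4.2.3 and the first paragraph of SAP 7.6.6.2 also keep the 6 weeks; SAP 7.4.2.3, for example, reads "radical cystectomy specifically and directly related to treatment related AEs within 6 weeks of the completion of neoadjuvant treatment". The window matches the surgery rule in Protocol 6.1, which requires cystectomy within 6 weeks of the last infusion. The result is to be reported by cohort with an exact 90% interval and compared by Fisher's exact test.

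The second paragraph of SAP 7.6.6.2 then says how to find these patients. The AE must be marked Caused Study Discontinuation "in AE CRF page, and with related to Nivolumab/Lirilumab, and patients do not have radical cystectomy surgery". There is no other operational rule in the SAP text.

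**The concern.** The rule and the definition identify different patients.

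- **No date test.** The surgery condition is that no cystectomy took place at all. A patient whose cystectomy is pushed past week 6 by a related AE, after one dose or two, has missed the endpoint's window but is not counted.
- **The flag is a different concept.** Study discontinuation is not the same as missing surgery. After the second dose there is no study drug left to stop, and a patient off treatment remains under observation, so a related AE could block surgery without the flag being set.

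This is the trial's only endpoint on whether drug toxicity keeps patients from timely curative surgery, and Protocol 13.1 describes the trial as asking whether adding lirilumab is feasible and safe. The missed case is foreseeable: Protocol 5.4 and 13.1.1 monitor Grade 2 immunologic AEs that have not settled by 6 weeks after the last dose, which is the period in which surgery is due. Omitting the date test can only lower the count. Nothing else in the SAP text would show the loss, because SAP 7.6.5 says only that "The number of patients who receive radical cystectomy will be summarized as well", without timing. SAP 2.1 gives the SAP precedence over the protocol's statistical section, and SAP section 8 declares no changes from it, so the departure is not disclosed.

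**Working it through.** The documents give no expected rate, power or threshold for this endpoint, so there is no stated figure to reproduce. The check compares the definition with the rule and then shows what a missed patient does to the estimate.

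**Step 1. Definition against rule**

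| Patient | Definition (Protocol 2.2, SAP 3.2) | Rule (SAP 7.6.6.2, second paragraph) |
|---|---|---|
| Cystectomy within 6 weeks | Not an event | Not an event |
| Cystectomy after 6 weeks because of a related AE | Event | Not an event |
| No cystectomy because of a related AE, flag set | Event | Event |
| No cystectomy because of a related AE, stays in follow-up, flag not set | Event | Not an event |
| No cystectomy because of progression or refusal, but a flagged related AE is present | Not an event | Event |

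Row 2 follows from the text alone. Rows 4 and 5 depend on how sites complete the flag. Three places support row 4. Protocol 5.3 gives patients without cystectomy an off-treatment visit. Protocol 8.2 says: "If a patient is removed from treatment for reason(s) other than progression, follow with regular tumor assessments per standard of care". SAP 7.6.6.3 lists as separate categories "TEAEs caused stopping study medications, TEAEs leading to early termination". Row 5 arises because nothing in the rule ties the flagged AE to the missed surgery.

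**Step 2. Interval method.** Inputs: n = 12 and n = 24 (SAP 7.1) and the Clopper-Pearson 90% interval, whose limits are the 5% quantile of Beta(x, n−x+1) and the 95% quantile of Beta(x+1, n−x). As a check, the maximum width is 0.509 for n = 12 and 0.361 for n = 24, which agrees with the 0.51 and 0.36 stated for the primary endpoint in Protocol 13.2.1.1 and SAP 7.4.1.

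**Step 3. Effect of missed late surgeries.** The counts are assumed, with no other events in the cohort. Each missed patient costs 1/12 = 8.3 points in Cohort 1 or 1/24 = 4.2 points in Cohort 2.

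| Late surgeries due to a related AE | By the definition (90% CI) | By the rule (90% CI) |
|---|---|---|
| Cohort 1, one | 1/12 = 8.3% (0.4% to 33.9%) | 0/12 (0% to 22.1%) |
| Cohort 1, two | 2/12 = 16.7% (3.0% to 43.8%) | 0/12 (0% to 22.1%) |
| Cohort 2, one | 1/24 = 4.2% (0.2% to 18.3%) | 0/24 (0% to 11.7%) |
| Cohort 2, two | 2/24 = 8.3% (1.5% to 24.0%) | 0/24 (0% to 11.7%) |

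**Step 4. Chance that at least one such patient occurs.** This is 1 − (1 − p)^n, where p is the chance that a patient has a late cystectomy because of a related AE. The values of p are assumptions.

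| p | Cohort 1, n = 12 | Cohort 2, n = 24 |
|---|---|---|
| 2% | 1 − 0.98^12 = 22% | 1 − 0.98^24 = 38% |
| 5% | 1 − 0.95^12 = 46% | 1 − 0.95^24 = 71% |
| 8% | 1 − 0.92^12 = 63% | 1 − 0.92^24 = 86% |

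**The case against.** **The two paragraphs of SAP 7.6.6.2 can be read together.** On this view the first supplies the window and the second only attributes the AE. A programmer might do this, but the surgery condition as written is the absence of any cystectomy, and a derivation should not rely on a reader adding a date.

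**The 6-week wording is not uniform.** In Protocol 13.2.3 the phrase runs "specifically and directly related to treatment related AEs within 6 weeks of the last dose of neoadjuvant treatment", so the window could be attached to the AEs rather than to the surgery, and the heading of SAP 7.6.6.2 suits a never-operated reading. Protocol 2.2 and SAP 3.2 settle this, because there the 6 weeks plainly qualifies the surgery.

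**The flag concern rests on an unseen CRF.** Cystectomy is part of the treatment plan (Protocol 6.1.3), so a site could reasonably tick the flag whenever an AE stops a patient before surgery. Protocol 8.3 also requires the reason for stopping treatment or observations on the eCRF, with unacceptable AEs among the options. This stands in part: the size of the flag problem is unknown. It does nothing for the missing date test.

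**The direction of the whole rule is not fixed.** This is correct. The date omission lowers the count, the flag may lower it, and the missing link between AE and missed surgery may raise it.

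**The consequence is limited.** The endpoint is secondary, no decision threshold uses it, the illustrated intervals overlap heavily, and the primary endpoint and interim safety rules are unaffected. All of this is fair. It bears on how serious the error is, not on whether the rule is right.

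**Conclusion.** The concern holds. As written, SAP 7.6.6.2 gives the wrong classification for any patient whose cystectomy is delayed past 6 weeks by a related AE, and it may misclassify patients who never have surgery. The first part needs no assumption beyond the text. The second depends on how sites use the flag, and the table templates, also a separate document, were not available. Each missed late surgery understates the rate by 8.3 points in Cohort 1 or 4.2 in Cohort 2. How many there would be cannot be derived from the documents. On an assumed 5% chance per patient, at least one is about an even chance in Cohort 1 (46%) and likely in Cohort 2 (71%). The point should be corrected before database lock, but it does not threaten the primary analysis.

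**What to change.** Replace the second paragraph of SAP 7.6.6.2 with a rule such as: *A patient is counted if, by 42 days after the last dose actually given, radical cystectomy has not been performed, and a nivolumab- or lirilumab-related AE is specifically and directly the reason.* Remove the study-discontinuation flag as a condition. Report delayed and never-performed surgery separately within the count, and add days from last dose to cystectomy to the surgery summary in SAP 7.6.5.

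The cost is one rewritten derivation and a few summary rows, using dose and surgery dates the study needs anyway. The documents show no field for why surgery was late or not done, so the reason must come from one added CRF item or from a medical review of the AE listing for patients with late or no surgery, completed before database lock. With 36 planned patients this is a small task. Dosing and surgery rules in the protocol do not change.
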